### 5.2. Baseline Definitions

- For all endpoints (except as noted in baseline definitions) the baseline value will be the latest pre-dose assessment with a non-missing value, including those from unscheduled visits. If time is not collected, Day 1 assessments are assumed to be taken prior to first dose and used as baseline.
- For Part A, baseline definitions defined in the table are applicable to each treatment period.
- Unless otherwise stated, if baseline data is missing no derivation will be performed and baseline will be set to missing. The mean of triplicate measurements at any given time point will be used as the value for that time point unless otherwise stated.

Parameter	Study Assessments Considered as Baseline			Baseline Used in Data Display
	Screening	Day -1	Day 1 (Pre-Dose)	
Safety				
Clinical Chemistry/ Haematology/ Urinalysis	X	X	X	Day 1
12-lead ECG	X	X 	X 	Day 1
Vital Signs	X	X	X 	Day 1
Pharmacokinetic				
PK Concentrations			X	Day 1
Pharmacodynamic				
PD Blood sample			X	Day 1
Target Engagement sample			X	Day 1

 ECG/Vital signs recordings will be performed in triplicate at visit. Use the mean of the triplicate measurements.

Unless otherwise stated, if baseline data is missing no derivation will be performed and baseline will be set to missing.

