## 2. SCHEDULE OF ACTIVITIES (SOA)

The schedules of activities (SOA) for Part A and Part B are presented in [Table 2](#) and [Table 3](#), respectively. The time points for the PK blood sample collection in Part A and Part B are presented in [Table 2](#) and [Table 4](#), respectively.

The timing and number of planned study assessments, including safety or PK assessments may be altered during the course of the study based on newly available data (e.g., to obtain data closer to the time of peak plasma concentrations) to ensure appropriate monitoring.

Any changes in the timing or addition of time points for any planned study assessments as a result of emerging pharmacokinetic data must be documented and approved by the relevant study team members and then archived in the sponsor and site study files. The competent authority (CA) and ethics committee (EC) will be informed of any safety issues that constitute a substantial amendment and require alteration of the safety monitoring scheme or amendment of the informed consent form (ICF). The changes will be approved by the CA and the EC before implementation.

There are times where the protocol requires more than one procedure to be completed at the same time point. In these instances the following will apply to post dose time points:

PK samples should take priority over other procedures scheduled at the same time point. As guidance, the preferred order of assessments is:

- Electrocardiograms (ECGs)
- Vital Signs
- PK blood sampling (nominal time)
- Other assessments e.g., physical exams,

Electrocardiograms (ECGs) should be taken prior to vital signs when both measurements are scheduled at the same time point. Other assessments, e.g., physical examinations etc, will be performed within the required time windows. All safety assessments will be timed and performed relative to the start of dosing.

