**Figure 1 Study design – Part A**

Separate participants will be enrolled into both cohorts of Part A.

The design for the 2 cohorts is as follows:

- Cohort 1: 5-way crossover design with the standard capsule. Each participant will receive single ascending oral doses of either GSK2983559 or placebo in a 4:1 ratio according to the randomisation schedule, in study periods 1 to 5, in a blinded manner.
- Cohort 2: 4-way crossover design with the enteric capsule for single ascending dose, including an additional period for assessing GSK2983559 under fed conditions (period 5 – open-label).

During the blinded part, each participant will receive single ascending oral doses of either GSK2983559 or placebo in a 3:1 ratio according to the randomisation schedule, in study periods 1 to 4, in a blinded manner.

If dose levels 6-9 are not investigated, Cohort 2 will only be used for evaluating the effect of food. It will be an open-label 2-way crossover design.

- Cohorts 1 and 2 will be dosed sequentially, incorporating sentinel participants: Cohort 1 will complete all 5 dosing periods before Cohort 2 begins.
- Following completion of Cohort 1 and before starting Cohort 2, a GSK internal safety board (independent of DEC) will be reviewing the data.
- Based on emerging PK data, all doses may not be investigated.
- There will be a at least 48-hour washout period between each dose escalation step but the washout period may be extended depending on emerging data.

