### 11.5.2. Reporting Standards

General

 
The current GSK Integrated Data Standards Library (IDSL) will be applied for reporting, unless otherwise stated (IDSL Standards Location: https://spope.gsk.com/sites/IDSLLibrary/SitePages/Home.aspx):             
 
4.03 to 4.23: General Principles
 
5.01 to 5.08: Principles Related to Data Listings
 
6.01 to 6.11: Principles Related to Summary Tables
 
7.01 to 7.13: Principles Related to Graphics
 
 
 
Do not include subject level listings in the main body of the GSK Clinical Study Report. All subject level listings should be located in the modular appendices as ICH or non-ICH listings
 
All data displays (Tables, Figures & Listings) will use the term "Subject" which reflects CDISC and GSK Data Display Standards terminology.
 

Formats

 
All data will be reported according to the actual treatment the participant received, unless otherwise stated.
 
GSK IDSL Statistical Principles (5.03 & 6.06.3) for decimal places (DP's) will be adopted for reporting of data based on the raw data collected, unless otherwise stated.
 
Numeric data will be reported at the precision collected on the eCRF.
 
The reported precision from non eCRF sources will follow the IDSL statistical principles but may be adjusted to a clinically interpretable number of DP's.
 

Planned and Actual Time

 
Reporting for tables, figures and formal statistical analyses:             
 
Planned time relative to dosing will be used in figures, summaries, statistical analyses and calculation of any derived parameters, unless otherwise stated.
 
The impact of any major deviation from the planned assessment times and/or scheduled visit days on the analyses and interpretation of the results will be assessed as appropriate.
 
 
 
Reporting for Data Listings:             
 
Planned and actual time relative to study drug dosing will be shown in listings (Refer to IDSL Statistical Principle 5.05.1).
 
Unscheduled or unplanned readings will be presented within the subject's listings.
 
 
 

Unscheduled Visits	

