## 11.10.5. Safety Tables

Safety: Tables					
No.	Population	IDSL / Example Shell	Title	Programming Notes	Deliverable [Priority]
Adverse Events (AEs)					
3.1.	Safety	AE1CP	Summary of All Adverse Events by System Organ Class and Preferred Term: Part A	ICH E3	SAC
3.2.	Safety	AE5A	Summary of All Adverse Events by Maximum Grade / Intensity by System Organ Class and Preferred Term: Part A	ICH E3	SAC
3.3.	Safety	AE5A	Summary of All Drug-Related Adverse Events by System Organ Class and Preferred Term and Maximum Intensity: Part A	ICH E3	SAC
3.4.	Safety	AE15	Summary of Common ( $\geq 10\%$ ) Non-serious Adverse Events by System Organ Class and Preferred Term (Number of Participant and Occurrences) : Part A	FDAAA, EudraCT	SAC
Serious and Other Significant Adverse Events					
3.5.	Safety	AE16	Summary of Serious Adverse Events by System Organ Class and Preferred Term (Number of Subjects and Occurrences) : Part A	FDAAA, EudraCT	SAC
3.6.	Safety	AE3	Summary of Adverse Events Leading to Permanent Discontinuation of Study Treatment or Withdrawal from Study by System Organ Class and Preferred Term /by Overall Frequency: Part A	IDSL	SAC
Laboratory: Chemistry					
3.7.	Safety	LB1	Summary of Chemistry Changes from Baseline: Part A	ICH E3	SAC

Safety: Tables					
No.	Population	IDSL / Example Shell	Title	Programming Notes	Deliverable [Priority]
3.8.	Safety	LB17	Summary of Worst Case Chemistry Results by PCI Criteria Post-Baseline Relative to Baseline: Part A	ICH E3	SAC
Laboratory: Hematology					
3.9.	Safety	LB1	Summary of Hematology Changes from Baseline: Part A	ICH E3	SAC
3.10.	Safety	LB17	Summary of Worst Case Hematology Results by PCI Criteria Post-Baseline Relative to Baseline: Part A	ICH E3	SAC
Laboratory: Urinalysis					
3.11.	Safety	LB1	Summary of Urine Concentration Changes from Baseline: Part A	ICH E3	SAC
3.12.	Safety	UR1	Summary of Worst Case Urinalysis Results (Discrete or Character Values) Post-Baseline Relative to Baseline: Part A	ICH E3	
Laboratory: Hepatobiliary (Liver)					
3.13.	Safety	LIVER1	Summary of Liver Monitoring/Stopping Event Reporting: Part A	IDSL	SAC
3.14.	Safety	LIVER10	Summary of Hepatobiliary Laboratory Abnormalities: Part A	IDSL	SAC
ECG					
3.15.	Safety	EG1	Summary of ECG Findings : Part A	IDSL	SAC
3.16.	Safety	EG10	Summary of Maximum QTc Values Post-Baseline Relative to Baseline by Category: Part A	IDSL	SAC

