## 11.10.6. Safety Figures

Safety: Figures					
No.	Population	IDSL / Example Shell	Title	Programming Notes	Deliverable [Priority]
Adverse Events					
3.1.	Safety	AE10	Plot of Common ( $\geq 10\%$ ) Adverse Events and Relative Risk: Part A	IDSL	SAC
Laboratory					
3.2.	Safety	LIVER14	Scatter Plot of Maximum vs. Baseline for ALT: Part A	IDSL	SAC
3.3.	Safety	LIVER9	Scatter Plot of Maximum ALT vs. Maximum Total Bilirubin: Part A	IDSL	SAC
3.4.	Safety	SAFE_01	Individual Profile Plots for Liver Function Tests : Part A	Page by liver function test (ALT, AST, ALKP, BILI) Scheduled & Unscheduled Visits to be presented Panel by subject Lower reference line ULN, High Reference Line PCI as y-axis allows. Label reference line clearly on figure or in legend	SAC
3.5.	Safety	SAFE_02	Box Plot of Liver Function Tests by Period: Part A	Page by liver function test (ALT, AST, ALKP, BILI) Scheduled visits only	SAC

Safety: Figures					
No.	Population	IDSL / Example Shell	Title	Programming Notes	Deliverable [Priority]
3.6.	Safety	SAFE_01	Individual Profile Plots for Renal Function Tests: Part A	Page by renal function test (Blood Urea Nitrogen, Calcium, Creatinine, Gamma GT, Potassium, Sodium, Blood Glucose – fasted, Urea) Scheduled & Unscheduled Visits to be presented Panel by subject LLN and ULN to be included as y-axis allows Label reference line clearly on figure or in legend	SAC
3.7.	Safety	SAFE_02	Box Plot of Liver Function Tests by Period: Part A	Page by renal function test (Blood Urea Nitrogen, Calcium, Creatinine, Gamma GT, Potassium, Sodium, Blood Glucose – fasted, Urea) Scheduled Visits Only	SAC

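### Part A resets the laboratory baseline in every period and defines no study baseline, so a late change is not credited to its dose and a cumulative change in haemoglobin, haematocrit or creatinine can go unflagged

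*SAP*

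**What the plan says.** SAP 5.2 states that "the baseline value will be the latest pre-dose assessment with a non-missing value, including those from unscheduled visits", and for Part A that "For Part A, baseline definitions defined in the table are applicable to each treatment period". The SAP defines no second baseline anchored before the first dose of the study.

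Tables 3.7 and 3.9 (SAP 11.10.5) give changes from baseline for chemistry and haematology. Tables 3.8 and 3.10 give worst case by PCI criteria. The title of Table 3.8 is "Summary of Worst Case Chemistry Results by PCI Criteria Post-Baseline Relative to Baseline: Part A", and Table 3.10 is the haematology counterpart.

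The PCI limits are in SAP 11.8.1. In the direction that matters here, three are expressed only as a change from baseline: a haemoglobin fall of 25 g/L, a haematocrit fall of 0.075 and a creatinine rise of 44.2 µmol/L. The transaminase, alkaline phosphatase and bilirubin limits are absolute multiples of the upper limit of normal (ULN).

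Under Protocol 5.1, participants leave the unit after the 48 h assessments. On the interval between doses it says: "There will be a at least 48-hour washout period between each dose escalation step". It also allows that interval to be extended. Cohort 1 has five periods. SAP 2.1 records that Cohort 2 received two of its four planned single doses.

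**The concern.** Change in laboratory values is part of the primary endpoint. With a baseline that restarts in each period, the tabulated change covers only the window from pre-dose to 48 h. A change that emerges later is first measured at the next period's Day -1 or pre-dose sample. There it counts as baseline, so it is not a post-baseline result for the earlier dose and it cancels out of the next period's change.

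Gradual drift is cut up in the same way: each period shows its own small step and no table shows the total. This matters most where the PCI limit is itself a change from baseline, because no absolute limit then picks up the accumulated value.

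The comparison with placebo is also touched. In Cohort 1, sequences 2 to 5 (8 of 10 participants) receive placebo after at least one active dose, so a late effect of active drug can enter a placebo-period baseline.

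**Working it through.** The plan states no figure that depends on the baseline rule, so there is none to reproduce. The check applies the SAP 5.2 rule and the SAP 11.8.1 limits to constructed series. Step sizes are illustrative assumptions.

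**Sampling gap.** I read the Part A schedule as giving post-dose laboratory samples at 8 h (chemistry), 24 h and 48 h; the column positions are not fully clear in my copy. Periods last at least 4 days (Protocol 5.1), so at the shortest interval the gap from the 48 h sample to the next dose is 4 - 2 = 2 days. Part A lasts about 11 weeks per participant. Taking off the longest screening (28 days) and follow-up (14 days) leaves 77 - 28 - 14 = 35 days, or 35 / 5 = 7 days per period, and a gap of 7 - 2 = 5 days. The unobserved window is therefore about 2 to 5 days on these assumptions.

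**How many periods are exposed.** Protocol Table 5 gives 10 - 2 = 8 active participants in each Cohort 1 period. Periods 1 to 4 precede another period: 8 × 4 = 32 planned active participant-periods.

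**Haemoglobin falling 10 g/L after every dose and not recovering.** Flag if the fall exceeds 25 g/L. Entries are falls in g/L for Periods 1 to 5.

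| Timing of each step | Fall at pre-dose | Fall at post-dose samples | Fall from period baseline | Fall from first-dose baseline | Flagged, period baseline | Flagged, first-dose baseline |
|---|---|---|---|---|---|---|
| Within 48 h | 0, 10, 20, 30, 40 | 10, 20, 30, 40, 50 | 10 in each | 10, 20, 30, 40, 50 | 0 of 5 | 3 of 5 |
| After 48 h | 0, 10, 20, 30, 40 | 0, 10, 20, 30, 40 | 0 in each | 0, 10, 20, 30, 40 | 0 of 5 | 2 of 5 |

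In the second row the follow-up visit shows a total fall of 50 g/L. Against the Period 5 baseline that is 50 - 40 = 10 g/L, still unflagged; against the first-dose baseline it is flagged.

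**Creatinine rising 15 µmol/L per period, limit 44.2.** The period baseline shows at most 15 in any period: 0 of 5 flagged. Against the first-dose baseline, steps within 48 h give 15, 30, 45, 60, 75 (3 of 5), and delayed steps give 0, 15, 30, 45, 60 (2 of 5).

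**A single step larger than the limit.** If a 30 g/L haemoglobin fall develops after 48 h and persists, it is flagged only when it follows the last dose and is seen at follow-up. After any earlier dose it becomes the next baseline.

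**Average step at which a first-dose baseline would flag the total (limit / number of periods).**

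| Parameter | 5 periods (Cohort 1) | 2 periods (Cohort 2 as dosed) |
|---|---|---|
| Haemoglobin, g/L | 25 / 5 = 5 | 25 / 2 = 12.5 |
| Haematocrit | 0.075 / 5 = 0.015 | 0.075 / 2 = 0.0375 |
| Creatinine, µmol/L | 44.2 / 5 = 8.84 | 44.2 / 2 = 22.1 |

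Under the period baseline, a step that appears within 48 h must itself exceed the full limit to be flagged.

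**The case against.** A period baseline is a reasonable choice in a crossover. It ties the change to the dose or placebo given in that period, and the study is descriptive with no hypotheses. In a fixed ascending sequence a study baseline mixes the current dose with earlier doses, repeated blood sampling and time. That stands, and it is why the period baseline should remain primary.

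A reader might go further and infer that no change or worst-case table ever counts a delayed or cumulative change. The documents do not support that. Changes within 48 h appear in their own period, and only the running total is lost. A change after the last dose can be caught at the follow-up visit, which has no later baseline. Most PCI limits are absolute, so a value that stays high after the next dose meets them whatever the baseline. It might read as unchanged in a relative-to-baseline table, but the shell is not in the documents. Table 3.14, Figures 3.3 to 3.6 and Listings 19 and 20 can also show raised values, and individual safety data were reviewed at each dose-escalation meeting (SAP 3.1).

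A reader might also infer that a post-dose Day 1 value can become the baseline, because SAP 5.2 says: "If time is not collected, Day 1 assessments are assumed to be taken prior to first dose and used as baseline". That would need the time to be uncollected and the nominal label to be ignored. The protocol states: "All safety assessments will be timed and performed relative to the start of dosing". SAP 11.5.2 states: "Planned time relative to dosing will be used in figures, summaries, statistical analyses and calculation of any derived parameters, unless otherwise stated". The SAP 5.2 table also labels its Day 1 column as pre-dose. I do not make that a point.

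Two backstops are weaker than they look. A clinically significant laboratory abnormality is an adverse event under Protocol Appendix 4, but treatment-emergent status ends one day after treatment stops (SAP 11.4.2). An event first seen at the next Day -1 would be treatment-emergent for neither period unless it later worsened. Unscheduled samples between periods are left out of summary tables and figures (SAP 11.5.2), although SAP 5.2 lets them serve as baseline.

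**Conclusion.** The gap is real and limited. With no study-level baseline, Tables 3.7 and 3.9 do not attribute a change emerging after 48 h to the preceding dose. Tables 3.8 and 3.10 can also miss a cumulative fall in haemoglobin or haematocrit, or a cumulative rise in creatinine. In the illustrations this is 0 of 5 periods flagged, against 2 or 3 of 5 with a first-dose baseline.

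This rests on three assumptions: the change persists from period to period, the steps are of the assumed size, and laboratory sampling within a period ends at 48 h. The 32 participant-periods count where a late change could be absorbed. They say nothing about how often one occurs, and the documents give no basis for estimating that. The shorter the actual interval between doses, the smaller the room for a late change; the loss of the running total does not depend on it.

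This is an inexpensive improvement to the reporting, not a fault in choosing a period baseline.

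**What to change.** Keep the period baseline as primary. In SAP 5.2, define a study baseline as the last non-missing value before the first study dose. For liver chemistry, creatinine, haemoglobin and haematocrit, add rows to Tables 3.7 to 3.10 giving change and worst case by PCI criteria against that baseline. In this supplementary display, count all later values as post-baseline, including the Day -1 and pre-dose values of subsequent periods and the follow-up visit.

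The cost is SAP wording and extra table rows, using samples already in the schedule. The drawback is interpretive: in an ascending-dose sequence a change from the study baseline cannot be attributed to a single dose. Every Cohort 1 sequence contains four active doses, so no participant supplies a drug-free reference for drift. A footnote should say so.

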### 5.3. Multicentre Studies

This is a single centre study.

### 5.4. Examination of Covariates, Other Strata and Subgroups

There are no covariates, strata or subgroups to be investigated in this study.

### 5.5. Multiple Comparisons and Multiplicity

No adjustments for multiplicity will be required.

## 5.6. Other Considerations for Data Analyses and Data Handling Conventions

Other considerations for data analyses and data handling conventions are outlined in the appendices:

Section	Component
11.3	Appendix 3: Assessment Windows
11.4	Appendix 4: Study Phases and Treatment Emergent Adverse Events
11.5	Appendix 5: Data Display Standards & Handling Conventions
11.6	Appendix 6: Derived and Transformed Data
11.7	Appendix 7: Reporting Standards for Missing Data
11.8	Appendix 8: Values of Potential Clinical Importance

## **6. STUDY POPULATION ANALYSES**

### **6.1. Overview of Planned Study Population Analyses**

The study population analyses will be based on the “Screened” or “Randomised” population, unless otherwise specified.

Study population analyses including analyses of subject’s disposition, protocol deviations, demographic and baseline characteristics, prior and concomitant medications, and exposure and treatment compliance will be based on GSK Core Data Standards. Details of the planned displays are presented in [Appendix 10: List of Data Displays](#).

## **7. SAFETY ANALYSES**

The safety analyses will be based on the “Safety” population, unless otherwise specified.

### **7.1. Adverse Events Analyses**

Adverse events analyses including the analysis of adverse events (AEs), Serious (SAEs) and other significant AEs will be based on GSK Core Data Standards. The details of the planned displays are provided in [Appendix 10](#): List of Data Displays.

### **7.2. Clinical Laboratory Analyses**

Laboratory evaluations including the analyses of Chemistry laboratory tests, Hematology laboratory tests, Urinalysis, and liver function tests will be based on GSK Core Data Standards. The details of the planned displays are in [Appendix 10](#): List of Data Displays.

### **7.3. Other Safety Analyses**

The analyses of non-laboratory safety test results including ECGs and vital signs will be based on GSK Core Data Standards, unless otherwise specified. The details of the planned displays are presented in [Appendix 10](#): List of Data Displays.

## 8. PHARMACOKINETIC ANALYSES

### 8.1. Primary Pharmacokinetic Analyses

#### 8.1.1. Endpoint / Variables

PK plasma concentration-time data for the prodrug GSK2983559 and active moiety GSK2668176 will be listed, no statistical analysis will be conducted. Summary statistics of the prodrug GSK2983559 and active moiety GSK2668176 concentrations by nominal blood sampling time will be determined.

PK data will be summarised for Parts A by randomised treatment.

Refer to [Appendix 5: Data Display Standards & Handling Conventions \(Section 11.5.3 Reporting Standards for Pharmacokinetic\)](#).

#### Overview of Planned Pharmacokinetic Analyses

Endpoints	Untransformed				Log-transformed			
	Summary		Individual		Summary		Individual	
	T	F	F	L	T	F	F	L
Pharmacokinetic								
Plasma Drug concentration	Y	Y 	Y 	Y				

#### NOTES:

- T = Table, F = Figure, L = Listings, Y = Display generated.
  - Summary = represents TF related to any summaries (i.e. descriptive statistics) of the observed raw data.
  - Individual = represents FL related to any displays of individual participant observed raw data.
- 1: Linear and Semi-Log plots will be created on the same display.  
2: Separate Mean ( $\pm$  SE) and Median plots will be generated.

PK plasma concentrations for 5-ABT and N-Ac-5-ABT (adjusted to 5-ABT concentration based on molecular weight (MW)) will be listed, no statistical analysis will be conducted.

#### 8.1.1.1. Drug Concentration Measures

Refer to [Appendix 5: Data Display Standards & Handling Conventions \(Section 11.5.3 Reporting Standards for Pharmacokinetic\)](#)

